**Stressor Paradigm:** MISTiC paradigm while the child is lying in the MRI scanner; includes two judges (one male, one female). After consent, youth are separated from their parents and taken for completion of questionnaires (approximately 20 minutes). Youth are taken to a private changing room to change into hospital scrubs prior to moving to the MRI scanner. An MRI-safe respiration belt and pulse oximeter and/or EKG electrodes are positioned for autonomic assessment and the child is given ear plugs, a button response box for math task, and an emergency call button. Youth rest and/or watch a video of their choosing during structural MRI sequences (6-10 minutes), then lie quietly with eyes open for a 5-minute scan with no video or audio material. They are then given an overview of the speech task and are told that they have 5 minutes to prepare. MRI data are collected during the 5 minutes of speech prep, following which the child is introduced to two judges who are visible on the child's video screen and who ask the child to perform their 5 min speech. No MRI data are collected during speech performance. At the end of the speech, the judges give the child instructions for the math performance section, and the child performs multiple-choice math problems that appear on the video screen using the button response box. MRI data are collected during math performance and judges remain visible on the screen during math performance. Following the judged math, judges leave the screen and youth rest or watch a video for 10 minutes during diffusion scanning. Finally, children perform another set of multiple-choice math problems with no judges present (photo of the same judges turned away) while MRI data are collected. Children are removed from the scanner and immediately complete a stress questionnaire and a debriefing session. Saliva samples are collected every 10-20 minutes throughout the session, including between scan segments, to assess dynamic changes in stress-related hormones. In the scanner, this involves handing a long collection sponge to the child which hangs out of the mouth to avoid any possibility of choking since the child is lying supine. We have used this method successfully in a previous study collecting saliva in the scanner environment. Following debriefing, the child will change back into their own clothing and return to the lobby to complete additional questionnaires for 30 min while being sampled for cortisol every 10 min.

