Task-based analysis: Math under social evaluative stress In first level analyses (single subject, single-run), math performance will be modeled for each participant using a voxel-wise multiple regression analysis with a task predictor (math trials vs. blank trials), 24 regressors for head motion (Satterthwaite et al., 2013) and additional regressors to model censored data points (motion spikes). In subsequent analyses, we will explore the utility of including other time varying individual differences variables (e.g., heart rate, respiration) that are known to contribute to the BOLD signal. However, since these measures are expected to vary by stress condition, removing the effects of these physiological variables may unintentionally remove effects of interest. Particular care will be taken to reduce the confound of head motion by censoring (identifying as artifact) any data point with absolute motion greater than 2 mm (1 voxel) or a framewise displacement greater than 0.5 mm, as well as the immediately preceding and following data points. Data points with DVARS values exceeding the

individual's 75th percentile plus two times the interquartile range will also be censored. Participants with more than 25% of data points censored for artifact will be excluded from further analyses.

Second level analyses (single-subject, multiple runs) will test the within-subject contrast of math performed with judges (social evaluative stress) relative to math performed alone (without social evaluation) to identify brain regions differentially activated by social evaluative stress. Based on prior literature, we will examine activation in 5 *a priori* regions of interest, including "pain-related" brain regions (dorsal anterior cingulate [dACC], left and right anterior insula) and "safety-related" or regulatory brain regions (ventromedial prefrontal cortex [vmPFC], and left and right dorsolateral prefrontal cortex [dlPFC]). For each subject, the mean percent change in MR signal (averaged across voxels) between judged math and math alone will be extracted from each of these 6 regions. This analysis will generate the 6 task-related brain activation outcome variables (listed in section 4.3) for each participant.

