cortex (left and right vmPFC and dlPFC). To determine whether connectivity varies as a function of stress, we will compare connectivity during the speech preparation scan to connectivity during the baseline resting state scan. Preprocessing steps will include motion correction, unwarping, and eddy-current correction. An initial voxel-wise multiple regression analysis will be performed to remove effects of head motion (24 predictors), and estimates of CSF and white matter signals (2 predictors) from each subject's data. Initial analyses will not include a predictor for global signal given evidence that the inclusion of global signal may falsely introduce anticorrelations in the data (Murphy et al., 2009; Saad et al., 2012). However, in exploratory analyses, we will examine the degree to which the results change when global signal is included in the model.

First-level (single-subject, single run) connectivity analyses on the residualized data will include the time course for a seed region and predictors for censored data points. Two separate regression models will be run, one using the bilateral amygdala as the seed region, and the other seeding connectivity in the hypothalamus.

Second-level (single-subject, multiple-runs) analyses will test the within-subject contrast of connectivity during anticipatory stress (speech preparation) relative to baseline resting state for each seed-region. Masks of a priori target brain regions of interest will be applied to resultant contrast maps to extract stress-related connectivity in the bilateral vmPFC and left and right dlPFC for each individual. This analysis will generate the 6 connectivity-related brain outcome variables (2 seed regions x 3 target regions) for each participant. Because difference scores (speech preparation minus baseline) can mask the direction of connectivity effects (positive vs. negative correlations), follow-up simple-effects analyses will assess connectivity separately in the speech preparation and resting state periods, using the same a priori seed and target regions. These follow-up simple-effects analyses will allow us to interpret the directionality of connectivity effects.

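### The connectivity clean-up fits the motion regressors before censoring enters the model, unlike the task analysis; if flagged volumes are in that first fit, shared motion signal can survive in the retained volumes

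*Combined protocol and SAP*

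**What the plan says.** Section 15.1, connectivity analysis of speech preparation, describes two successive regressions.

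- Step 1: "An initial voxel-wise multiple regression analysis will be performed to remove effects of head motion (24 predictors" together with "estimates of CSF and white matter signals (2 predictors". That makes 24 + 2 = 26 nuisance terms. No censoring term is listed.
- Step 2: the "connectivity analyses on the residualized data will include the time course for a seed region and predictors for censored data points".

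The task analysis in the same section is built differently. Its single first-level model holds the task predictor, the 24 motion regressors and "additional regressors to model censored data points (motion spikes".

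The censoring rule appears only under the task analysis. It flags a volume for absolute motion above 2 mm or "a framewise displacement greater than 0.5 mm, as well as the immediately preceding and following data points", and a DVARS criterion also applies. The exclusion rule is there too: "Participants with more than 25% of data points censored for artifact will be excluded from further analyses".

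Two scans feed the connectivity outcomes (section 5.2, stressor paradigm). For the first, "MRI data are collected during the 5 minutes of speech prep"; for the second, children "lie quietly with eyes open for a 5-minute scan with no video or audio material". Two seeds and three target regions give 6 primary connectivity outcomes, each the within-child difference between the scans. Follow-up analyses then look at each scan separately.

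**The concern.** Fitting in sequence equals fitting jointly only when the two sets of predictors are orthogonal. Motion terms and spike indicators are not, because volumes are flagged largely on their motion. High-motion volumes have high leverage in step 1. If their signal does not follow the same linear relation to the motion terms as the quiet volumes, they pull the coefficients, and every retained volume is then corrected with the wrong coefficients. Spike predictors added in step 2 take the flagged volumes out of the seed model but cannot undo this. If the artefact is shared by seed and target, so is the correction error, and it looks like coupling.

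At stake are the 6 connectivity outcomes, including the vmPFC-amygdala coupling of Hypothesis 1 (section 2.3). A child preparing a speech may move differently from a child lying quietly, and the size of that difference may vary with condition, sex or puberty, the factors tested in section 15.3. Randomising condition does not remove this, because motion in the scanner arises after randomisation.

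**Working it through.** The plan states no figure on this point, so there is none to reproduce. The check has four parts.

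**1. Algebra.** Let X hold the intercept and the 26 nuisance terms, with rows c flagged and rows k retained. Write y = Xβ + s + e, where s is non-zero only on flagged rows. It is the departure of the spike signal from the linear relation that holds in the quiet volumes.

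- As written, with flagged rows in step 1: b = (X'X)⁻¹X'y, so E(b) − β = (X'X)⁻¹X_c's_c. The retained residuals then carry −X_k(X'X)⁻¹X_c's_c. If seed and target share s, both carry the same term.
- Joint fit: one indicator per flagged volume fits that row exactly, so b = (X_k'X_k)⁻¹X_k'y_k, and s drops out.
- If one linear relation holds in all volumes, s = 0 and the two orders agree in expectation.

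**2. What the plan's own rules leave in.** If spikes are scattered at rate p and each flagged volume takes its two neighbours with it, the expected censored share is 1 − (1 − p)³.

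| Spike rate p | Expected share censored | Against the 25% limit |
|---|---|---|
| 2% | 1 − 0.98³ = 5.9% | retained |
| 5% | 1 − 0.95³ = 14.3% | essentially all retained |
| 10% | 1 − 0.90³ = 27.1% | about one third retained (simulated) |
| 20% | 1 − 0.80³ = 48.8% | none retained (simulated) |

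The expected share reaches 25% at p = 1 − 0.75^(1/3) = 9.1%.

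**3. Size in a single scan.** The documents supply the 24 motion terms, the neighbour censoring, the 25% limit and the 5-minute scans. The rest is assumed: 300 volumes (a repetition time of 1 s, which the plan does not give), spike size 6 SD, motion weight .3, scattered spikes and true connectivity 0. Response is the spike-volume slope as a share of the low-motion slope.

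| Spike rate | Response 0% | 30% | 60% | 80% |
|---|---|---|---|---|
| 2% | about .02 | about .01 | – | – |
| 5% | about .10 | about .05 | about .015 | about .004 |

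The joint fit stays within about .01 of zero.

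Two further simulations assume a different artefact: 5 or 10 noise SD, shared by seed and target, in 150 or 300 volumes.

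- Two-volume bursts with neighbours censored: two-step slope .059 to .360 at about 10% censored, and .196 to .495 at about 24%. The joint fit lay between −.009 and .005 over all cells. With no such artefact, both orders were within .007 of zero.
- Isolated one-volume jerks with neighbours censored: about 0 to .05 at 8% censored, 0 to .21 at 15%, and .02 to .23 at 22%. The joint fit stayed within about .01.

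Direction and remedy agree in all three. Size follows the assumed artefact, which the documents do not fix.

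**4. From one scan to the outcome.** The outcome is preparation minus rest, so its bias is B_prep − B_rest, which is zero when the two scans carry equal bias. The bias in a planned test is the difference in (B_prep − B_rest) across condition, sex or puberty. The documents give no motion data, so neither quantity can be computed. The separate-scan follow-ups carry B_prep or B_rest in full.

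**The case against.** The strongest reply has four parts.

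- **The plan does not say that step 1 uses every volume.** True; that is an inference. It rests on a list of step 1 terms without censoring, on censoring being named in step 2 and in the task model, and on nothing in the documents that drops, down-weights or interpolates flagged volumes first. One sentence from the sponsor could settle it.
- **Motion control is already extensive.** The plan has 24 motion terms, displacement and DVARS censoring, neighbour removal, a 25% exclusion, spike predictors in the seed model, and a power scenario with 40 of 200 children lost to movement (section 15.2). These measures limit the size. They do not remove the mechanism, and using censoring on top of the 24 terms presumes that those terms do not capture spikes fully.
- **Large figures depend on harsh inputs.** Without the neighbour and 25% rules, the 6 SD set-up gives .12 and .16 at 10% and 20% spikes with a 30% response, and .20 and .29 with no response. A reader might infer that correlations of that order are to be expected. The documents do not support this: with scattered spikes, about two thirds of children at the 10% rate and all at the 20% rate would be excluded. Slopes near .5 need a shared 10 SD artefact just under the limit. One qualification remains: the 25% rule is written under the task analysis and is not repeated for the connectivity scans.
- **The outcome is a difference between scans.** Bias common to both cancels. This stands, and it is the main limit on the point.

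**Conclusion.** The concern holds as a conditional one. As written, the order of steps can leave motion-related correlation between seed and target if flagged volumes enter the first regression and if spike artefact is not fully linear in the 24 motion terms. Under the 6 SD assumptions with the plan's rules applied, the single-scan size runs from about 0 (few spikes, or a near-linear response) to about .10 at 5% spikes, and somewhat higher for children close to the 25% limit. Larger assumed artefacts give larger values. A joint fit gives about 0 throughout.

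A reader might infer that the 6 primary connectivity outcomes, or the tests on them, are shown to be biased. They are not. The contrast is affected only if motion differs between the two scans, and the planned tests only if that difference varies with condition, sex or puberty. The plan does not establish that motion is equal, and nothing in the documents shows that it differs. The separate-scan follow-ups have no such cancellation and are the more exposed. The change is worth making because it removes an avoidable bias of unknown size at almost no cost.

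**What to change.** Fit the seed time course, 24 motion, CSF, white-matter and censored-volume regressors in one first-level model, as the task analysis already does for its own predictors. Equivalently for this purpose, estimate the nuisance coefficients on uncensored volumes only. State in the connectivity paragraph which volumes enter the nuisance fit, and that the censoring rules and the 25% exclusion given under the task analysis apply to both the speech-preparation and the resting scan.

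The cost is a reordered pipeline step and a few sentences of text. No new data are needed.

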### 2.3 Study Aims:

The current study examines the neural response, as well as the cortisol hormonal response to social evaluative stress across the transition to puberty. We use a modified version of the Trier Social Stress Test (TSST) in the MRI scanner (called the Minnesota Imaging Stress Test in Children; MISTiC) to elicit social evaluative stress. In this project, we will randomly assign youth to complete this testing under one of three social buffering conditions: presence of a parent, presence of an experimenter (stranger), or no social support present (standard imaging condition).

The **long-term goal** of our research is to enrich understanding of stress regulation and its role in human development. The **overall objective** of this project is to understand normative processes in stress regulation and their neurobiological correlates as children leave childhood and become more autonomous in adolescence. The **central hypothesis** of this project is that early adolescence is a period of time when parental buffering wanes in efficacy, leaving many youth experiencing a relative dearth of relationships that can provide powerful stress buffers.

**The aim of the current study is to delineate changes in brain activation in response to social buffering by parents over the pubertal transition.**

**Hypothesis #1:** Parental social buffering will result in increased activation in brain regions associated with safety (e.g. vmPFC) and lower activation in brain regions involved in fear and pain (e.g., insula, amygdala, hypothalamus), as well as tighter coupling between the vmPFC and amygdala activity, but these relationships will wane with pubertal development.

**Hypothesis #2:** Neural activity associated with social buffering will mediate the effectiveness of physiological buffering by social partners.

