## 15.0 Statistical Considerations

*15.1 Data Analysis Plan:*

Preliminary Analyses to Determine Covariates Needed for Primary Analyses. The purpose of collecting data on potential covariates is to identify variables that are correlated with both the independent variable (social buffering condition, sex, pubertal stage) and the primary outcome measures. Those covariates that are associated with the independent and outcome variables will be controlled for in the primary analyses. Those that are not will be used to describe the sample, but will not need to be included in the analyses to obtain unbiased estimates. For each potential covariate, we will conduct correlations or t-tests with pubertal stage, and t-tests, ANOVAs, or chi-square tests (as appropriate) with sex and condition. If data do not confirm to modeling assumptions, we will use nonparametric analogs instead.

Preliminary Analyses of Imaging Data to Yield Primary Outcome Measures: fMRI data will be analyzed in FSL software (version 5.0.10) to generate voxel-wise contrast maps. Mean signal values will be extracted from these maps in a priori regions of interest for every participant using the methods described below. These preliminary analyses are used to generate the fMRI outcome variables of interest. The values of these outcome variables for each participant will be used in the general statistical analyses described in the next section. In total, these preliminary analyses will yield 6 primary task-related outcome variables, and 6 primary connectivity-related outcome variables.

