15.2 Power Analysis: For the power analysis for the primary analyses, we calculated the minimum detectable effect size (MDES) assuming  $n = 200$ ,  $\alpha = .05$ , and power = .80 with 12 covariates in our model. Power was estimated in R (R Core Team) using the pwr library (Champely, 2018). A power analysis was performed to quantify the minimum detectable effect size ( $f^2$ ) for a three-way interaction between social buffering condition, sex, and pubertal stage within a multiple regression model controlling for the 12 covariates, all two-way interactions, and the main effects (the most complex model considered in our primary analysis, see Equation 1 below). Assuming these conditions, we should be able to detect an  $f^2$  of 0.056. In

other words, adding the three-way interaction to a model containing the covariates and all lower order interactions and main effects, the three-way interaction would need to explain an additional 5.6% of the variability to be detected. This falls between Cohen's criteria for a small ( $f^2 = .02$ ) and medium effect ( $f^2 = .15$ ) (Cohen, 1988). With a sample size of 200, even if we lose 40 of the participants to movement artifact for the imaging analyses, assuming all the previous conditions but a sample size of 160, we will still have an  $f^2$  of .070, or still within a small-medium effect size. As the number of covariates decreases, the size of the MDSE will decrease. Therefore, this represents a conservative estimate of the power for our primary analyses as we are likely to have fewer covariates in our models and will use multiple imputation to correct for missing data. For the two-way interaction and main effects models, described below, the power will be larger than these reported values as the models will be simpler.

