### 15.3 Statistical Analysis of MRI and non-MRI Outcome Variables:

The following is a list of the analyses that we will perform on the outcome measures. They are classified as to whether they are the primary or mediational analyses. All statistical analyses will be performed in R.

The primary analyses will consist of a series of multiple regression models. For each dependent variable, variation in neural activity, cortisol response, and heart rate response, we will begin by testing the three-way interaction between social buffering condition, sex, and pubertal stage for all outcomes. If the three-way interaction is not significant, we will then examine all two-way interactions. If the two-way interactions are not significant, we will then examine main effects only models. If the three-way interaction is significant, we will not examine any other model. If condition is significant as an interaction or as a main effect, we will examine all pairwise comparisons using Tukey's Honestly Significant Difference test.

Multiplicity of testing. We will correct for multiple comparisons using the Benjamini-Hochberg (BH) correction. The BH method works by controlling the false discovery rate, and relative to the Bonferroni's correction is more powerful, while still adequately protecting against Type I error (Williams, Jones, & Tukey, 1999).

Mediational Analysis. When changes in activity of brain regions differ by condition or condition by pubertal status and we also see condition or condition by pubertal status differences for cortisol, or heart rate, then we will examine whether brain activity differences mediate the neuroendocrine or autonomic differences. This will be examined using path analysis, while controlling for covariates identified in the preliminary

covariate analysis, and will be estimated using the lavaan package in R (Rosseel, 2012).

The significance of all indirect effects will be assessed using bias-corrected 95% confidence intervals (Efron & Tibshirani, 1986), where confidence intervals that are non-overlapping with zero will be considered significant.

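### Section 15.2's 80%-power effect sizes are for one unadjusted test; they are not shown to hold, or to be conservative, under the Benjamini-Hochberg correction in 15.3

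*Combined protocol and SAP*

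**What the plan says.** Section 15.2 takes n = 200, α = .05, power .80 and 12 covariates. It derives the smallest f² detectable for one condition × sex × pubertal stage interaction: 0.056, or .070 if 40 participants are lost to movement. It places both between Cohen's small (.02) and medium (.15) benchmarks. It then says that "this represents a conservative estimate of the power for our primary analyses", for two reasons: fewer covariates are likely, and missing data will be multiply imputed. For the two-way and main-effect models it adds that "the power will be larger than these reported values as the models will be simpler". It does not mention multiplicity.

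Section 15.3 applies the test more widely: "we will begin by testing the three-way interaction between social buffering condition, sex, and pubertal stage for all outcomes". It names neural activity, cortisol response and heart rate response as the dependent variables. Section 15.1 counts the neural ones: "these preliminary analyses will yield 6 primary task-related outcome variables, and 6 primary connectivity-related outcome variables". That makes 12 + 2 = 14 outcomes. Section 15.3 then states: "We will correct for multiple comparisons using the Benjamini-Hochberg (BH) correction". It does not say which outcomes are corrected together, whether the two-way and main-effect steps belong to the family, or what q is.

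**The concern.** The decision rule that was powered is one test at α = .05. The rule that will be used is BH across several outcomes, where a result must usually meet a stricter threshold. Neither reason given for calling the estimate conservative concerns multiplicity.

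At stake is how a null result is read. If 80% power at f² = .056 is taken to apply to each primary outcome, a non-significant interaction in one brain region looks better supported than it is. The gap cannot be worked out from the plan, because it depends on q, on the family and on how many outcomes are truly affected. The α = .05 in 15.2 belongs to one power calculation and is not a stated q.

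The same gap affects condition by puberty, the interaction in Hypothesis 1 (section 2.3), which predicts that "these relationships will wane with pubertal development".

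**Working it through.** **Inputs.** From 15.2: n = 200 or 160, α = .05, power .80, 12 covariates, f² = .056 and .070, R's pwr library. From 4.1 and 5.1: three conditions and continuous pubertal stage. From 15.1 and 15.3: 12 brain outcomes, cortisol and heart rate.

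**Degrees of freedom.** Main effects 2 + 1 + 1 = 4; two-way terms 2 + 2 + 1 = 5; three-way terms 2. With 12 covariates there are 23 predictors. So u = 2 and v = n − 24 = 176 or 136.

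**The plan's own figures.** Power = P(F′ > F crit), where F′ is noncentral F(u, v, λ) and λ = f²(u + v + 1), as in pwr.
- n = 200: λ = .056 × 179 = 10.02, power .809; f² for power .80 is .0548.
- n = 160: λ = .070 × 139 = 9.73, power .795; f² for power .80 is .0709.

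The stated values are therefore approximately right for one unadjusted test. Using u = 3 and v = n − 4 matches the print slightly better (.0556 and .0699). With that choice, BH at q = .05 over 14 outcomes gives .46 to .77, so the result does not depend on it.

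**BH power at the stated effects.** Simulated step-up BH with independent outcomes. Each cell gives per-outcome power with one / half / all outcomes affected. The family m and q are assumptions.

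| q | m | n = 200, f² = .056 | n = 160, f² = .070 |
|---|---|---|---|
| .05 | 6 | .58 / .69 / .78 | .56 / .67 / .76 |
| .05 | 12 | .49 / .68 / .78 | .47 / .66 / .76 |
| .05 | 14 | .47 / .68 / .78 | .45 / .66 / .76 |
| .10 | 6 | .68 / .80 / .87 | .67 / .78 / .86 |
| .10 | 12 | .59 / .79 / .87 | .57 / .77 / .86 |
| .10 | 14 | .57 / .79 / .87 | .55 / .77 / .86 |

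At q = .05 the loss against .809 or .795 is about 3 points if all outcomes are affected. If one is affected it is 22 points (.809 − .585) to 34 points (.795 − .453). Outcome correlations of .3 or .5 (n = 200, m = 12 or 15) give about .47 to .77.

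**Effect needed for 80% power under BH.** The lower end is all outcomes affected (simulated). The upper end is the strictest step, α = q/m in the noncentral F formula.

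| q | n | All affected | Strictest step, m = 6 / 12 / 14 |
|---|---|---|---|
| .05 | 200 | .058 | .082 / .093 / .095 |
| .05 | 160 | .075 | .107 / .121 / .124 |
| .10 | 200 | .047 | .072 / .082 / .085 |
| .10 | 160 | .061 | .093 / .107 / .110 |

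**The covariate argument.** With no covariates there are 11 predictors, v = 188 or 148, and the single-test f² falls only to .0513 or .0651. Under BH at q = .05 (m = 6 or 14), power at the stated effects is then about .50–.62, .71–.73 and .81–.82 for one, half and all outcomes affected. Dropping every covariate thus offsets the correction only if all outcomes are affected.

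**Condition by puberty.** This model has 21 predictors, so v = 178 or 138. Single-test power at the stated effects is .814 or .801. Treated as a stand-alone test under BH at q = .05, it is .48–.79 (n = 200) and .46–.77 (n = 160).

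**Variance wording.** f² = ΔR²/(1 − R²full), so ΔR² = f²(1 − R²full). This is at most .056/1.056 = .053.

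**The case against.** **BH costs little when many outcomes respond, and q may be .10.** Both are true. Hypothesis 1 expects effects in several regions, so exactly one affected outcome is an extreme case. At q = .10 nothing is lost if all outcomes are affected, and about 1 to 2 points if half are. But 15.2 assumes nothing about the number affected and 15.3 does not give q, so the plan cannot rely on the favourable case.

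**Some effect will be found.** At q = .05 with half the outcomes affected, the chance of detecting at least one of them is .93 to .99. This stands. The point here is power for each outcome.

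**Imputation is also offered as a reason.** At best it restores complete data at n = 200, and the n = 200 figures above already assume that. How motion-excluded participants are handled is a separate matter.

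**The two-way sentence is correct.** As a relative statement it is: .814 against .809, and .801 against .795. It is incomplete only because the comparison is with an unadjusted test.

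**Stronger readings.** A reader might infer that the power arithmetic is wrong, or that the trial is too small. The documents support neither. The single-test values reproduce. The largest corrected effect for families up to 14 at q = .05 is .124, still below .15, so the small-to-medium description survives. Nor can one say that power falls below 80% whatever the rule: at q = .10 with all outcomes affected it is .86 to .87.

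**Conclusion.** The concern holds for the 80% figure and for the word conservative. Both are supported for a single unadjusted test, and neither is shown for the BH-corrected primary analyses. With 12 covariates, q = .05, independent outcomes and families of 6 to 14, per-outcome power at the stated effects is below .80 in every case computed, from .45 (one of 14 affected, n = 160) to .78 (all affected, n = 200). At q = .10 the range is .55 to .87.

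These ranges are not bounds. The plan fixes neither q nor the family. Section 3.1 also lists respiration as a primary outcome, and a family of 15 lowers the bottom of the q = .05 range to about .44. Families that include the two-way and main-effect tests were not computed.

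This should be corrected. It affects the stated power and the definition of the significance rule, not the sample size.

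**What to change.** In 15.3, state q and the BH family: which outcomes are corrected together, and whether the two-way and main-effect tests are included.

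In 15.2:
- Label .056 and .070 as unadjusted single-test values.
- Add the BH-corrected detectable effect for the chosen q and family, as a range from all outcomes affected to the strictest step (second table above). For example, with q = .05 and a family of 12 it is about .058 to .093 at n = 200 and .075 to .121 at n = 160.
- Restrict the word conservative to the single unadjusted test.
- Say that the sentence on two-way and main-effect power is relative to that same unadjusted test.
- Minor, same paragraph: 15.2 says "the three-way interaction would need to explain an additional 5.6% of the variability to be detected". Replace this with ΔR² = f²(1 − R²full), at most 5.3%.

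The cost is a few sentences and a short recalculation, with no change in sample size. The stated figures will look less favourable if q = .05 is chosen.
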